2.2.3 Other variables

For subjects ≥ 2 years of age (based on DRC data):

- Responder rate (the percentage of subjects who have a $\geq 50\%$ reduction in seizure frequency per 28 days from Baseline for POS)
- Absolute change in seizure frequency (total seizures) per 28 days from Baseline to the end of the Evaluation Period
- Percent change in seizure frequency (total seizures) per 28 days from Baseline to the end of the Evaluation Period
- Seizure freedom over the Evaluation Period
- Proportion of seizure-free days over the Evaluation Period

For subjects < 2 years of age or subjects with typical absence seizures based on DRC seizure counts:

- Seizure freedom rate over the Evaluation Period (all types) by visit and by time intervals (6 months, 12 months, etc.)
- Proportion of seizure-free days over the Evaluation Period (all types) and by time intervals (6 months, 12 months, etc.)
- Absolute worsening in ADF of total seizures (all types)
- Percent worsening in ADF of total seizure (all types)
- A descriptive summary of seizure frequency by visit based on the DRC data will be also provided for these subjects

In addition, for subjects < 2 years of age (based on EEG data [recorded at least 24 hours]) or subjects with typical absence seizures (based on EEG data):

- Responder rate for total POS defined as the percentage of subjects with a $\geq 50\%$ reduction in ADF of POS recorded on EEG
- Absolute change in ADF of total seizures (all types)
- Percent change in ADF of total seizures (all types)
- Seizure freedom (rate and proportion)
- Absolute worsening of other types of seizures
- Percent worsening of other types of seizures

For subjects with typical absence seizures:

- Number and type of non-absence seizures

For all subjects:

The other variables include the following:

- Physical examinations (including Tanner staging, if applicable depending on subject's development status)
- Neurological examinations
- Psychiatric and mental status
- Laboratory tests (hematology, biochemistry including hepatic monitoring of ALT, AST, ALP, total bilirubin, and GGT, and endocrinology [follicle-stimulating hormone, luteinizing hormone, thyroid-stimulating hormone, triiodothyronine, and tetraiodothyronine] for all subjects and urinalysis for subjects for whom sample collection is feasible)
- ECG
- Vital signs (blood pressure, pulse rate, and body temperature)
- Body weight
- Height and head circumference
- Plasma concentrations of BRV and phenytoin (if applicable)

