3.10.3 Seizures and seizure categories

Each seizure code in the clinical database will be mapped to exclusively 1 of the following seizure types based on the 1981 ILAE classification: IA, IA1, IA2, IA3, IA4, IB, IB1, IB2, IC, IIA, IIB, IIC, IID, IIE, IIF, or III.

With regard to cluster seizures, study sites are to report the number of cluster episodes rather than reporting the estimated number of individual seizures. Therefore, no imputation will be applied for the seizure counts corresponding to reports of cluster seizures. In all the efficacy analyses, clusters will be counted as one seizure (i.e. 1 cluster = 1 seizure) and assigned to the corresponding seizure type.

For the evaluation of this study the categorization of subjects to different seizure categories and the analysis by these seizure categories is essential.

Four different seizure categories need to be distinguished and defined:

- **POS – Partial-onset Seizure**

Subjects are categorized as POS subjects at ScrV if either Partial-Onset Seizure is entered on the “ILAE Seizure Classification History” eCRF page at ScrV or if it has been reported on “Historical Seizure Count” eCRF page for the last 3 weeks prior to ScrV with non-zero value.

- **PGS – Primary Generalized Seizure**

Subjects are categorized as PGS subjects at ScrV if either Typical Absence Seizure, Atypical Absence, Myoclonic, Clonic, Tonic, Tonic-clonic or Atonic Seizure is entered on the “ILAE Seizure Classification History” eCRF page at ScrV or if one of these seizure types has been reported on “Historical Seizure Count” eCRF page for the last 3 weeks prior to ScrV with non-zero value.

- **PGS* – Primary Generalized Seizure excluding Typical Absence**

Subjects are categorized as PGS* subjects at ScrV if either Atypical Absence, Myoclonic, Clonic, Tonic, Tonic-clonic or Atonic Seizure is entered on the “ILAE Seizure Classification History” eCRF page at ScrV or if one of these seizure types has been reported on “Historical Seizure Count” eCRF page for the last 3 weeks prior to ScrV with non-zero value.

- **Typical Absence Seizure**

Subjects are categorized as Typical Absence subjects at ScrV if either Typical Absence Seizure is entered on the “ILAE Seizure Classification History” eCRF page at ScrV or if it has been reported on “Historical Seizure Count” eCRF page for the last 3 weeks prior to ScrV with non-zero value.

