Central reader interpretation = “Abnormal”; >0 seizure counts	Use “Normal”; 0 counts	No problem

Calculation of average daily frequency (ADF) of seizures

Average daily frequency (ADF) of seizures based on the EEG data (from central reader or eCRF) is calculated differently for 1-hour and 24-hour EEG:

For 1-hour EEG:

$$\text{ADF} = \text{Number of seizures from EEG data source considered for 1 hour EEG} \times 24$$

For 24-hour EEG (with missing information on interpretable hours):

$$\text{ADF} = \text{Number of seizures from EEG data source considered for 24 hour EEG}$$

For 24-hour EEG (with information on interpretable hours):

$$\text{ADF} = \frac{\text{Number of seizures from EEG data source considered for 24 hour EEG}}{\text{Number of interpretable hours}} \times 24$$

The ADF will be calculated including all seizure types and additionally for POS seizures and PGS seizures, separately.

For certain endpoints, multiple EEG assessments are to be combined. In this instance, for n assessments, average ADF is given as:

$$\text{Average ADF} = \frac{\sum_{i=1}^n \text{ADF}_i}{n}.$$

Calculation of absolute change/worsening in ADF of seizures

Absolute change in ADF is calculated as:

$$\text{Absolute Change in ADF} = \text{Baseline ADF} - \text{postBaseline ADF}.$$

Both absolute changes will be calculated, with ADF including all seizure types and additionally based on POS seizures only.

Absolute worsening in PGS ADF is calculated as:

$$\text{Absolute Worsening in PGS ADF} = \text{postBaseline PGS ADF} - \text{Baseline PGS ADF}.$$

Calculation of percent change/worsening in ADF of seizures

Percent change in ADF is calculated as:

$$\text{Percent Change in ADF} = \frac{\text{Absolute Change in ADF}}{\text{Baseline ADF}} \times 100.$$

Both percent changes will be calculated, with ADF including all seizure types and additionally based on POS seizures only.

Percent worsening in PGS ADF is calculated as:

$$\text{Percent Worsening in PGS ADF} = \frac{\text{Absolute Worsening in PGS ADF}}{\text{Baseline PGS ADF}} \times 100.$$

Calculation of response

Response is defined to be equal to 1 for Percent Change in ADF $\geq 50\%$ and 0 for $< 50\%$. Both responses will be calculated, with percent change in ADF including all seizure types and additionally based on POS seizures only.

For subjects < 2 years of age response is based on the 24-hour EEGs performed over the Evaluation and Down-Titration Period separately.

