6.3 History of epilepsy

6.3.1 Epileptic seizure profile

The number and percentage of subjects experiencing each seizure category at any time prior to study entry will be summarized based on the ILAE Seizure Classification History eCRF.

The overall number and percentage of subjects with a history of Type I (POS), Type II (PGS), or Type III (Unclassified) seizures will also be summarized. A subject will be classified as having a history of Type I seizures if the subject has a history of Type IA, IB, or IC seizures. A subject will be classified as having a history of Type II seizures if the subject has a history of Type IIA1, IIA2, IIB, IIC, IID, IIE, or IIF seizures.

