9.1 Seizure based variables based on EEG data

EEG summaries will be presented by age group (< 2 years (24 hour EEG), ≥ 2 years (1 hour EEG)) and by seizure category. Outputs will explicitly restrict the analyses on 24 hour EEG to subjects < 2 years of age. If we have 1 hour EEG assessments for subjects categorized as < 2 years of age according to the Baseline age, we will perform sensitivity analyses in which we present results only by age group (< 2 years, ≥ 2 years), irrespective of the type of EEG performed. The POS and PGS* results for subjects ≥ 2 years will be missing, because EEG is only performed for subjects within Typical Absence seizure category there.

All analyses will be based on data assessed in Evaluation Period only.

Absolute and percent change in ADF will be summarized by age group and seizure category. Additionally, absolute and percent change in POS ADF will be summarized similarly.

Number of responders based on all seizure categories and the corresponding responder rate will be presented. Same will be presented for response based on POS only.

The number and percentage of seizure free subjects (Seizure freedom) will be presented.

Absolute and percent worsening based on PGS seizure types will be summarized.

All raw EEG seizure counts and derived efficacy variables will be listed.

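### In typical-absence subjects the EEG worsening variable for other seizure types counts the absences themselves, so falling absences offset rising non-absence generalised seizures

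*SAP*

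**What the plan says.** SAP Section 2.2.3 lists two EEG variables for subjects under 2 years or with typical absence seizures: "Absolute worsening of other types of seizures" and "Percent worsening of other types of seizures". For typical-absence subjects alone it adds "Number and type of non-absence seizures".

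For EEG data, Section 3.10.3.1 derives the average daily frequency (ADF) in three forms: "The ADF will be calculated including all seizure types and additionally for POS seizures and PGS seizures, separately". Its only EEG worsening formula is post-Baseline PGS ADF minus Baseline PGS ADF, with a percent version that divides by Baseline PGS ADF. Section 9.1 then plans the matching summary: "Absolute and percent worsening based on PGS seizure types will be summarized".

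Section 3.10.3 places typical absence among the PGS seizure types. It describes the PGS category as PGS* (generalised seizures without typical absence) together with Typical Absence. On who has EEG data at age 2 years or more, Section 9.1 says that POS and PGS* results will be missing there, "because EEG is only performed for subjects within Typical Absence seizure category there".

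**The concern.** The label in Section 2.2.3 speaks of other seizure types. For a subject with partial-onset seizures (POS), PGS is indeed another type and the formula fits. For a typical-absence subject it does not, because PGS contains the seizure that defines the subject's category. That covers the whole EEG stratum aged 2 years or more, and any typical-absence subject under 2.

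At stake is what the table can tell a reader. A negative worsening value could mean that absences fell while myoclonic or tonic-clonic seizures stayed level, or that absences fell while those seizures rose. The summary cannot separate the two. The SAP defines PGS* but derives no EEG ADF for it. The variable that would answer the question directly, on non-absence seizures, has no derivation in Section 3.10.3.1 and no table in Section 9.1 or 9.2.

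**Working it through.** The SAP states no figure on this point, so there is none to reproduce. The check applies its formulas to assumed counts.

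**Inputs.** From Section 3.10.3.1: 1-hour ADF = count × 24; absolute change = Baseline − post-Baseline; PGS worsening = post-Baseline PGS ADF − Baseline PGS ADF; percent worsening = worsening ÷ Baseline PGS ADF × 100. From Section 3.10.3: PGS = typical absence + PGS* types. The seizure counts are assumptions.

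**General form.** Let A be typical absences and G other generalised seizures on a 1-hour EEG, with 0 for Baseline and 1 for post-Baseline.

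- PGS worsening = 24 × [(A1 − A0) + (G1 − G0)].
- Worsening without typical absence = 24 × (G1 − G0).
- The planned value is negative whenever the fall in A exceeds the rise in G, zero when they are equal, and positive but diluted when absences fall by less than G rises.
- With no POS and no unclassified seizures, PGS ADF equals total ADF, so PGS worsening = −(total change) exactly, in absolute and percent terms.

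**One case in full.** Baseline 6 absences and 0 others: 6 × 24 = 144. Post-Baseline 2 absences and 2 others: (2 + 2) × 24 = 96. Planned worsening: 96 − 144 = −48 per day; −48 ÷ 144 = −33%. Non-absence seizures: 0 × 24 = 0 to 2 × 24 = 48, so +48 per day.

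**Range of assumed counts** (absence + other, Baseline to post-Baseline):

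| Counts | PGS ADF | Planned PGS worsening | Worsening without typical absence |
|---|---|---|---|
| 10+0 to 4+3 | 240 to 168 | −72 (−30.0%) | +72 (percent undefined) |
| 10+1 to 4+3 | 264 to 168 | −96 (−36.4%) | +48 (+200%) |
| 10+0 to 4+6 | 240 to 240 | 0 (0%) | +144 (percent undefined) |
| 10+0 to 4+8 | 240 to 288 | +48 (+20%) | +192 (percent undefined) |
| 10+0 to 10+3 | 240 to 312 | +72 (+30%) | +72 (percent undefined) |

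The first two rows reverse the sign, the third shows nothing, the fourth understates the rise, and the last, with absences unchanged, is correct in absolute terms. Percent worsening without typical absence cannot be computed when its Baseline is 0.

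**Do other outputs carry the same information?**

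- The shift tables of new seizure types (Sections 3.10.3.1 and 9.2) use daily record card (DRC) data. They show whether a type is present, not how often, so they miss a rise in a type already present at Baseline.
- DRC worsening (Section 3.10.3.1) uses total seizure frequency and nets in the same way.
- Raw EEG and DRC counts are listed but not summarised by type.
- New POS lies outside PGS. On EEG it appears only in the POS and total ADF summaries.

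**The case against.** The strongest reply is that other types may simply mean other than POS. Section 2.2.3 pairs POS and total-seizure variables in lists shared by infants and typical-absence subjects, and PGS is the natural complement of POS. The separate variable "Number and type of non-absence seizures" would be partly redundant if other types already meant non-absence. This reading is plausible and fits POS subjects. It does not rescue the measure for typical-absence subjects: without POS or unclassified seizures the table repeats the total change with the opposite sign, and the variable meant for this group has no derivation or table.

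Three stronger inferences are tempting but not supported.

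- A reader might infer that emerging non-absence seizures are hidden throughout the reporting. They are not. A new myoclonic type recorded in the diary would count as a new incidence in the shift tables, and raw counts are listed.
- A reader might infer a departure from the protocol, since Section 3.11 reports no changes. The protocol is not at hand, so its definition of other types is unknown and no departure can be shown.
- A reader might take the coding list in Section 3.10.3 ("IA, IA1, IA2, IA3, IA4, IB, IB1, IB2, IC, IIA, IIB, IIC, IID, IIE, IIF, or III"), set against Section 6.3.1 ("history of Type IIA1, IIA2, IIB, IIC, IID, IIE, or IIF seizures"), as proof that typical and atypical absence cannot be told apart. Section 3.10.3 assigns subjects to categories from eCRF pages on which the two are separate entries. This is a separate coding inconsistency and does not support the present point.

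It is also fair to object that the SAP does not show EEG counts being recorded by generalised subtype. The fix has to be conditional on that.

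**Conclusion.** The point holds in limited form. For typical-absence subjects, who make up the whole EEG stratum aged 2 years or more, the variable labelled as worsening of other types is computed from a total that includes typical absences. A fall in absences offsets or outweighs a rise in other generalised seizures. In subjects without POS or unclassified seizures the variable adds nothing to the total-change summary.

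The size in any subject depends on the counts. In the assumed examples the planned value runs from −96 to +72 per day while non-absence seizures rise by 48 to 192 per day. The direction of the error follows from the SAP's definitions alone; only the counts are assumed. Complete masking needs absences to fall by at least as much as the other generalised seizures rise.

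The reach is modest. Efficacy variables are exploratory and summaries descriptive, so no test is affected. EEG analysis covers only LTFU subjects, and Table 3-6 removes those from EP0065 and N01349 from the worsening analysis. The loss concerns frequency in one EEG summary, together with one listed variable that has no planned output.

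**What to change.** - **Sections 3.10.3.1 and 9.1.** Keep PGS worsening for POS subjects. For Typical Absence subjects, base it on seizures other than typical absence (PGS* types plus POS), where EEG counts are recorded by type. Report absolute worsening, because percent worsening is undefined when Baseline is 0.
- **Sections 3.10.3.1 and 9.2.** Add a derivation and a table from DRC data for the number and type of non-absence seizures in typical-absence subjects, giving 28-day adjusted frequency by type at Baseline and during the Evaluation Period. EP0065 and N01349 subjects have no Baseline diary data and would contribute only to the Evaluation Period column.
- **Separately,** reconcile the absence codes in Sections 3.10.3 and 6.3.1.

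The cost is SAP wording, one reprogrammed variable and one extra table. If EEG counts turn out not to be split by type, the first item cannot be done and the DRC table becomes the main output for this question; the SAP should then say that PGS worsening in Typical Absence subjects includes typical absences.

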9.2 Seizure based variables based on DRC data

Absolute and percent change in 28-day adjusted seizure frequency and in 28-day adjusted POS seizure frequency will be summarized for the Evaluation Period by seizure category. This summary will present both age groups to be consistent with EEG summary and worsening based on DRC. The corresponding number and percentage of responder in reduction of 28-day adjusted seizure frequency and 28-day adjusted POS seizure frequency will be presented separately.

For subjects < 2 years of age or ≥ 2 years of age with typical absence seizures, absolute and percent worsening will be presented. Additionally, the ADF will be summarized by age group, seizure category and visit/time period.

The proportion of seizure free days over Evaluation Period will be summarized using quantitative statistics. This summary will be repeated for proportion of seizure free days by visit and by 3-month time interval (including only subjects < 2 years of age or ≥ 2 years of age with typical absence seizures).

Number and percentages of Seizure freedom will be presented over Evaluation Period. This summary will be repeated for seizure freedom by visit and by 3-month time interval (including only subjects < 2 years of age or ≥ 2 years of age with typical absence seizures).

Shift tables presenting the incidences of new seizures will be prepared to show actual occurrences of new seizures as well as the percentages based on subjects under risk (subjects without particular seizure type at Baseline).

All raw DRC data and derived efficacy variables will be listed.

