2.3.1 Study design for DE subjects

The screening period comprises the screening visit (ScrV).

Directly enrolled subjects will begin receiving BRV in the Up-Titration Period at Titration Visit 1 (TV1) after all inclusion and exclusion criteria are met. The BRV dose will be titrated to optimize tolerability and seizure control. Subjects may enter the Evaluation Period after they have remained on the same daily dose (no lower than the minimum specified dose) for 7 ± 2 days that, in the opinion of the Investigator, has demonstrated acceptable tolerability and seizure control. Up to 3 TVs may be needed before entry into the Evaluation Period.

Evaluation Period starts with the Entry Visit (EV) followed by Minimal Evaluation Visits (MEV), Full Evaluation Visits (FEV), Yearly Evaluation Visits (YEV), possibly Unscheduled Visits (UV) and Early Discontinuation Visits (EDV), if applicable. For more detailed information of visits scheduled, see [Table 2-1](#)

Table 2-1: Visit sequence

DE subjects		
	Visit	Type of visit
	ScrV	Screening
W1	TV1 ^a	TV
W2	TV2 ^a	TV
W3	TV3 ^a	TV

All subjects		
First year follow-up		
M0	V1	EV ^b
M1	V2	MEV
M2	V3	FEV
M3	V4	MEV ^c
M4	-	-
M5	-	-

M6	V5	FEV
M7	-	-
M8	-	-
M9	V6	MEV ^c
M10	-	-
M11	-	-
Second and subsequent years follow-up^d		
M12	V7	YEV
M15	V8	MEV
M18	V9	FEV
M21	V10	MEV
and every 3 months thereafter	V11, V12, etc.	YEV, MEV, etc.

BRV=brivaracetam; EV=Entry Visit; FEV=Full Evaluation Visit; LTFU=long-term follow-up; M=Month; MEV=Minimal Evaluation Visit; ScrV=Screening Visit; TV=Titration Visit; V=Visit; W=Week; YEV=Yearly Evaluation Visit

Note: Visits at W1, W2, W3, and M0 will occur 7 ± 2 days after the previous visit; visits at M1, M2, and M3 will occur 30 ± 7 days after the previous visit; visits at M6, M9, M12, M15, M18, M21 and every 3 months thereafter will occur 90 ± 15 days after the previous visit.

“-” denotes that no visit is scheduled in that month.

^a All DE subjects must participate in at least TV1, but may participate in fewer than 3 TVs as described in Section 7.2.1 of the protocol.

^b For LTFU subjects, the EV is the final evaluation visit of the core study. For DE subjects, the EV represents the point of entry into the Evaluation Period.

^c Hepatic monitoring tests only will be performed as described in Section 9.5.1 of the protocol.

^d Subsequent years will follow the same visit schedule.

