2.3.4 Planned number of subjects and sites

N01266 is planned for a total enrollment of approximately 600 subjects, including at least 100 eligible DE subjects ≥ 4 years to < 17 years of age with POS.

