2.4 Determination of sample size

No formal sample size calculation was performed for this study. Originally, up to 500 subjects might have possibly enrolled in this study. The original number was based upon the assumption that 90% of the subjects having completed a core study will rollover into the present study.

Planned enrollment now includes approximately 600 subjects, including at least 100 DE subjects, with no change in the assumption regarding core study completion.

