3.2.3 Study periods

[Table 3–1](#) shows which study periods are applicable to DE and LTFU subjects:

This document cannot be used to support any marketing authorization application and any extensions or variations thereof.
PUBLIC COPY

Table 3-1: Study periods

Period		Screening Period	Up-Titration Period			Evaluation Period							Down-Titration Period	Safety Period		
Subjects	Visit	ScrV	TV1	TV2	TV2	EV	MEV	FEV	MEV	FEV	MEV	YEV	...	FV/EDV	DTV	SV
			V1	V2	V3	V4	V5	V6	V7	...						
Subjects	DE	x	x	x	x	x	x	x	x	x	x	x	x	x	(x)	(x)
	LTFU					x	x	x	x	x	x	x	x	x	(x)	(x)
	Early Discontinuations												x	x	x	x

(x) – only applicable if the subject does not switch to another BRV study or is taking marketed drug after FV

The study is divided into 5 periods: Screening Period, Up-Titration Period, Evaluation Period, Down-Titration Period, and the Safety Period.

There is a Screening Period for all DE subjects. For DE subjects, this comprises assessments performed prior to the first dose of BRV in N01266. So start date of Screening Period is date of written informed consent and end date is the day before first dose of BRV (TV1-1). Although, patients in LTFU studies will not attend a screening visit, the screening information comprises information collected at various assessments during the core study and consequently will have been collected at different times depending on the domain. Domain specific information is detailed in Section 3.3.

The Up-Titration Period is only applicable to DE subjects, and the start date is the date of the first dose of BRV. The following algorithm is used to determine the end date:

- If the subject enters the Evaluation Period, the date 1 day prior to the EV is the end date
- If the subject does not enter Evaluation Period, the Up-Titration Period ends on the date of the final dose of BRV

For the Evaluation Period, the start date is the date of the first dose of BRV on or after the EV date, and the following algorithm is used to determine the end date:

- If the subject continues the study until it ends, the Evaluation Period ends on the date of FV
- If the subject prematurely discontinues the study, the date of EDV is the end date

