Criterion 1: A subject completed the reported Time Period

- Up-Titration Period: for DE subjects only, if at least one eCRF during Up-Titration Period is entered (only Baseline/TV1, Baseline/TV1 and TV2 or Baseline/TV1, TV2 and TV3 could be entered, dependent on subject's individual titration)
- Evaluation Period: if the FV or EDV eCRF page (named FIN) is entered
- Down-Titration Period: if the eCRF DTV page is entered (DTV is the final visit for the Down-Titration Period)

Criterion 2: The seizure diary was completed for at least 90% of days from start date of the appropriate Time Period up to the day prior to the end date of the appropriate Time Period.

Criterion 3: All entered seizure codes have a count of 0 from the day after start date of appropriate Time Period (ie, not including the start date of appropriate Time Period) up to and including the end date of the appropriate Time Period. (If a seizure code is entered, a missing count will lead to a violation of this criteria, too.)

If one of the criteria is not fulfilled, Seizure freedom is defined to be equal to 0.

Seizure freedom will be based on DRC data collected over the Up-Titration, Evaluation and Down-Titration Period separately. All seizure types will be taken into account.

Calculation of Seizure freedom rate

Seizure freedom rate will be determined as follows:

$$\text{Seizure freedom rate of Time Period} = 100 \times \left[\frac{\text{Number of subjects who were seizure free over reported Time Period}}{\text{Number of subjects who entered reported Time Period with at least one DRC entry during the Time Period}} \right]$$

All seizure types will be taken into account.

Calculation of Seizure freedom by visit

The categorical variable Seizure freedom by visit is defined to be equal to 1 if the following criteria are fulfilled:

Criterion 1: The question "Have there been any seizures since the last visit?" has been answered with "No" and all entered seizure codes in the DCR have a count of 0 since prior visit. (If a seizure code is entered, a missing count will lead to a violation of this criteria, too.)

Criterion 2: The seizure diary was completed for at least 90% of days since prior visit. The percentage of days for which diary data were entered since the prior visit will be calculated as follows:

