9 EFFICACY ANALYSES

All presentation for efficacy parameters will be based on the FAS and will be summarized by age group (<2 years and ≥ 2 years of age) and seizure category as categorized in Section 4.8, and overall.

Efficacy variables will be assessed using the seizure count information recorded on the DRC and EEG data. Endpoints derived from the DRC will be summarized separately from those derived from the EEG. EEG data collected from 24-hour EEG and 1-hour EEG will be presented separately.

Details of the derivations for all efficacy variables are provided in Section 3.10.3.1.

All summaries of efficacy data are descriptive; no statistical testing will be performed.

All seizure data and derived endpoints will be listed. Data from Up-Titration Period (DE subjects only) and Down-Titration Period will be listed only, if not otherwise mentioned.

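### DE efficacy rates are conditional on getting through Up-Titration: the responder denominator is not stated, and no rate over all treated DE children is planned

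*SAP*

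**What the plan says.** **Entry.** SAP Section 2.3.1 lets a DE child into the Evaluation Period after 7 ± 2 days on the same daily dose that, "in the opinion of the Investigator, has demonstrated acceptable tolerability and seizure control". Section 3.2.3 foresees children who never get there: "If the subject does not enter Evaluation Period, the Up-Titration Period ends on the date of the final dose of BRV".

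**What is reported.** Section 9.2 states the period for the diary (DRC) change summaries: "percent change in 28-day adjusted seizure frequency and in 28-day adjusted POS seizure frequency will be summarized for the Evaluation Period by seizure category". The corresponding responders, the proportion of seizure-free days and seizure freedom follow in the same section. Section 3 has DE subjects analysed on their own as well as pooled.

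**Denominators.** For DRC seizure freedom, Section 3.10.3.1 divides by "Number of subjects who entered reported Time Period with at least one DRC entry during the Time Period". For response, it defines only who counts as a responder. Section 3.1 leaves percentage denominators to whatever suits the analysis.

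**Who belongs.** Section 3.5.3 puts in the FAS every Safety Set subject with a completed post-Baseline DRC or EEG. Section 4.6 says all dosed subjects with such a record go into the efficacy summaries.

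**Up-Titration data.** Sections 3.1 and 3.10.3.1 say Up-Titration data for DE subjects are summarised separately. Section 3.10.3.1 also derives response and seizure freedom for that period. Section 9 says: "Data from Up-Titration Period (DE subjects only) and Down-Titration Period will be listed only, if not otherwise mentioned".

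**The concern.** For DE children, a judgement that includes seizure control falls between Baseline (diary days from the Screening Visit to the first Titration Visit) and the period in which efficacy is measured. Children who do badly early, on seizures or on tolerability, are the ones likely not to pass. A rate computed only among those who pass answers a narrower question than how children started on BRV fared.

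This matters most in the DE cohort, planned as "including at least 100 eligible DE subjects", because these children had not previously enrolled in a pediatric BRV study and their start on BRV in this trial is observed. A reader who sees a DE responder rate under an FAS heading, with Section 4.6 in mind, would take it to cover every treated DE child with a diary. Sections 1 and 4.3 also allow interim outputs to support regulatory submissions.

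**Working it through.** The SAP gives no expected response rate and no Up-Titration failure share, and Section 2.4 states: "No formal sample size calculation was performed for this study". There is no figure to reproduce. The check is a reading of the rules, followed by bounds on assumed inputs.

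**1. Follow one child through the rules.** Take a DE child who receives BRV, completes a post-Baseline DRC and stops BRV in Up-Titration.
- FAS (3.5.3): in.
- Efficacy summaries according to 4.6: in.
- Average daily frequency (3.10.3.1) is calculated over the Evaluation Period, by visit and by 3-month interval. For the Evaluation Period the child has no value, hence no change and no response status.
- Seizure-freedom denominator for the Evaluation Period (3.10.3.1): out, because the child did not enter it.
- Responder denominator: not stated. If it is subjects with an Evaluation Period value, the child is out. If it is the FAS count, the child is in and is in effect a non-responder.
- Dropout rule (4.2): seizure outcomes use available diary days on BRV, which for this child are Up-Titration days only. The exposure-duration cohorts offered there are meant to remove the influence of earlier discontinuations, so they do not bring the child back.

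**2. What the unstated denominator is worth.** Assume 100 DE children in the FAS, q = 10% stopping in Up-Titration, and 36 responders among the 90 entrants. The same 36 responders give 36/90 = 40.0% or 36/100 = 36.0%, depending on a choice the SAP does not make.

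**3. Conditional rate against all-treated rate.** Let p be the rate among entrants, q the share of DE FAS subjects who stop in Up-Titration, and r the rate the stoppers would have had.

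All-treated rate = p(1 − q) + rq.

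Relative overstatement = p / [p(1 − q) + rq] − 1.

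With r = p this is 0. With r = 0 it is 1/(1 − q) − 1 = q/(1 − q), whatever p is. With p = 40% (assumed):

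| q (assumed) | Entrants per 100 | All-treated, r = 0 | All-treated, r = p/2 | All-treated, r = p | Maximum relative overstatement q/(1−q) |
|---|---|---|---|---|---|
| 5% | 95 | 38.0% | 39.0% | 40.0% | 5% |
| 10% | 90 | 36.0% | 38.0% | 40.0% | 11% |
| 15% | 85 | 34.0% | 37.0% | 40.0% | 18% |
| 20% | 80 | 32.0% | 36.0% | 40.0% | 25% |

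The largest gap in percentage points is p × q. For p from 30% to 50% it is 1.5 to 2.5 points at q = 5%, 3 to 5 at 10%, 4.5 to 7.5 at 15%, and 6 to 10 at 20%.

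**4. Would separate Up-Titration output close the gap?** Sections 3.1 and 3.10.3.1 promise summaries or derivations. Section 9 reduces Up-Titration efficacy data to listings unless stated otherwise, and 9.2 adds no Up-Titration table. By contrast, the laboratory, vital-sign and ECG sections (8.3, 8.4.1, 8.4.2) each say explicitly that the summary is repeated for Up-Titration. Even if the efficacy tables were produced, they would show two periods side by side and no rate over all treated DE children.

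**The case against.** The strongest defence is that the plan reports what it set out to report. The secondary objective is efficacy during long-term exposure, and the variables in Sections 2.2.2 and 2.2.3 run to the end of, or over, the Evaluation Period. For entrants the rate is a correct description. Follow-up (LTFU) subjects are selected too: they completed a core study and had to tolerate its minimum dose. Re-basing DE children alone would mix two populations in the pooled column. Efficacy is exploratory, uncontrolled and untested. The disposition table (5.1) shows how many children entered Up-Titration, how many went on to the Evaluation Period and why subjects discontinued, so a reader could work out the bound. All of this stands. It limits the consequence and is a reason to confine the added rows to the DE cohort.

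Four stronger readings are tempting but not supported:
- A reader might infer that efficacy is summarised for the Evaluation Period alone. Sections 3.1 and 3.10.3.1 provide for separate Up-Titration summaries or derivations, so the defect is a conflict with Section 9.
- A reader might infer that stoppers are shown to be excluded from the responder rate. That is written only for seizure freedom. For response it is the likely result of the derivation, and an FAS denominator remains possible.
- A reader might equate the entry condition with the outcome. Entry rests on a clinical opinion over about a week, whereas response is a reduction of at least 50% in 28-day adjusted frequency. Entrants were not already classed as responders.
- A reader might infer that the selection always favours BRV. A child may stop for intolerance while seizures are falling.

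What the defence does not answer is the conflict between the entry-based denominator and Section 4.6, the missing responder denominator, and the absence of any all-treated DE rate.

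**Conclusion.** The point holds in a limited form. DE change, response and seizure freedom in Section 9.2 are conditional on entering the Evaluation Period, and entry depends partly on early seizure control and tolerability. FAS children who stop in Up-Titration are outside the seizure-freedom denominator by rule and probably outside the responder denominator by derivation, against Section 4.6.

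The DE rates are expected to be higher than the rate among all DE children started on BRV. The relative overstatement lies between 0 and q/(1−q), provided stoppers would not have responded at a higher rate than entrants. The upper end requires every stopper to be a non-responder. Because q is not in the SAP, the actual size cannot be established, and it would be wrong to report the upper bound as the effect. This is a worthwhile, inexpensive clarification of a secondary, descriptive analysis and does not touch the primary safety objective.

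**What to change.** - In Sections 3.10.3.1 and 9.2, state the denominator of the DRC responder rate.
- For the DE cohort, add one responder row and one seizure-freedom row over all DE subjects in the FAS, counting those who stopped BRV in Up-Titration as non-responders and not seizure-free.
- Keep the current Evaluation Period rows and label them as conditional on entering that period.
- Reconcile Sections 3.1, 3.10.3.1, 4.6 and 9, so that it is clear whether Up-Titration efficacy data are tabulated or listed and who is in each efficacy summary.

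The added rows would still omit a treated DE child with no completed post-Baseline DRC, since that child is not in the FAS. A footnote giving the DE counts in the Safety Set and the FAS would show how many there are.

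The cost is SAP wording and one extra row per table, from data already collected. The downside is a slightly less favourable DE rate shown next to the existing one.
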